Cover page for clinicaltrials.gov

Study Title	Incorporating strategy training into naming
	treatment to improve generalization in
	aphasia
NCT Number	Not yet assigned
Document Description	Protocol and statistical analysis plan
Document Date	March 3, 2022

PARTNERS HUMAN RESEARCH COMMITTEE DETAILED PROTOCOL

Study Title: Incorporating strategy training into naming treatment to improve generalization in aphasia

I. BACKGROUND AND SIGNIFICANCE (including progress report and preliminary studies)

a. Historical background

Aphasia is an acquired communication disorder that results from damage to brain regions responsible for various language processes⁶³. Aphasia is a common sequela to stroke^{2,63} and can result in partial or total loss of spoken and written communication ability^{2,62}. Despite improvements over the past several decades in the treatment of aphasia, roughly 1 in every 250 people in the United States is currently living with aphasia⁶³, many of whom will live with the disorder for the rest of their lives. People living with aphasia often become dependent on their caregivers²⁸, do not return to work²⁸, experience depression⁴, and withdraw from activities that bring them joy and fulfillment²¹. Therefore, it is urgent to identify treatments that will result in meaningful improvements in the language abilities of people with aphasia (PWA).

There are eight clinical subtypes of aphasia, distinguished from one another by differences in their degrees of impairment in verbal fluency, auditory comprehension, and word/phrase repetition^{2,62}. Despite these differences, all PWA experience one common impairment: naming³⁶. Naming, also referred to as 'lexical retrieval' or 'word finding,' refers to one's ability to verbally identify objects⁶⁵. Successful naming requires a person to recognize a concept/object and then retrieve the word that matches the concept from their mental lexicon⁶⁵. Not only is successful naming essential to effective communication, but the severity of a PWA's naming impairment has been shown to be associated with the overall integrity of the language system⁷ as well as with measures of connected speech^{72,73}. The centrality of naming to effective communication and various language processes make naming an extremely common focus of aphasia treatment.

b. Previous Studies and Research Rationale

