Additional inclusion/exclusion criteria include the following: Eligible individuals must achieve a score of 4 or greater on the Auditory Verbal Comprehension Score, which is a subtest of the Western Aphasia Battery-Revised (WAB-R) for full enrollment/participation in the study. Eligible individuals must also name 1-146 of the 176 items correctly on the initial administration of the naming assessment for full enrollment/participation in the study. Individuals who name 0, or greater than 146 items will be excluded. These criteria will be assessed at the initial study visit, after informed consent has been obtained.

b. Source of subjects and recruitment methods

Individuals with aphasia will be recruited by referral from physicians, speech-language pathologists, and neuropsychologists. We will mail and email recruitment letters to neurologists and speech pathologists in the greater Boston area. Interested professionals will describe the study to the potential participants and ask them to contact the researcher if they are interested in participating in the experiment.

Individuals with aphasia will also be recruited from the MGH Institute of Health Professions Aphasia Center. SLPs will share study flyers with individuals with aphasia and ask if individuals are interested in meeting a member of the research team to learn more about the study. If they express interest, a member of the research team will be invited to come to the end of an upcoming scheduled therapy session to talk more about the study, or Aphasia Center staff can coordinate a meeting between the individual and a member of the study staff. It will be clearly communicated that the treating Speech language pathologist has no affiliation to the research study and that expressing or not expressing an interest to speak to research staff, in no way impacts the therapy services they receive in the MGH IHP Aphasia Center.

In addition, individuals with aphasia will be recruited via word of mouth, flyers, flyers/presentations at local aphasia centers, and emails to community health centers and via listservs (the American Speech-Language Hearing Association (ASHA) Special Interest Group 2 Neurogenic

Communication Disorders listserv, as well as the ASHA Special Interest Group 14 Cultural and Linguistic Diversity listserv). We will also recruit via Rally and the MGH IHP IRB-approved Recruitment Database.

IV. SUBJECT ENROLLMENT

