c. Treatment assignment and randomization. All study participants will receive the same treatment procedures. No assignment or randomization is required.

V. STUDY PROCEDURES

a. Study visits and parameters to be measured: Participants will have the option to participate at the MGH IHP, at their home, or via Enterprise Zoom.

Once participants are consented, the typical study sequences include (*also in Figure 1*): Each step is described in additional detail in the section that follows.

- 1) Pre-treatment: Completion of pre-treatment cognitive-linguistic assessments, naming probes, and spontaneous speech probes (sessions approximately 2 hours in length over an average of 3-5 days to mitigate any effect of fatigue on assessment performance).
- 2) During Treatment: Participation in the treatment for a period of eight weeks. All participants will receive the same treatment. Participants will receive in-person therapy at the MGH Institute of Health Professions, home visits, or virtual sessions (via Zoom). Participants will attend three 70-minute treatment sessions per week for eight consecutive weeks. Treatment sessions will be conducted by a certified SLP. Starting on Week 2, the first treatment session of each week will begin with a 30-minute assessment, consisting of a naming probe, a connected speech probe, and a strategy knowledge probe, in which the participant will be asked to provide the six strategy components. Treatment will stop at the end of the eight weeks, or after three consecutive naming probe performances over 90% accuracy, whichever occurs first.
- Post-treatment re-administration of assessments: Participants will complete the same cognitive-linguistic assessments, naming probes and spontaneous speech probes as they did pre-treatment within 20-30 days following the last treatment session. Sessions will last approximately 2 hours in length over an average of 3-5 days.
- 4) Post-treatment tests of retention: Participants will attend two additional post-treatment sessions one month and two months after the final treatment session. During each post-treatment session, participants will complete a 176-item naming assessment, one connected speech probe, and a strategy knowledge probe.

Phase 1) Pre-treatment:

a) Cognitive-linguistic assessments. Eligible and consented participants will complete a battery of standardized cognitive-linguistic assessment, including:

- The Western Aphasia Battery-Revised (WAB-R)⁴⁶,

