- (a) provide education on object naming,
- (b) work with the participant to develop strategies to quickly identify instances in which they are unable to name an object,
- (c)teach the participant to immediately begin generating feature words, i.e., circumlocuting, once they realize they are unable to name an object, and
- (d1) teach the participant the six types of feature words they can produce during circumlocution (i.e., the six SFA framework components, Figure 2 below). The clinician and the participant will work together to learn and memorize the six components. Once the participant is able to independently identify four of the six components across three sessions, *Strategy Education* will change as follows.

- The clinician will review steps (a c) and then,
- (d2) ask the participant to list the components. The clinician will provide reinforcement and cues for any strategy components the participant is unable to independently identify. The clinician will also ask the participant to describe any recent instances in which they had success using the strategy at home or out in the community.

Figure 2. Semantic Feature Analysis chart with the six strategy components

Naming Treatment Plus Strategy Application.

- (e) The clinician will place a picture of an object from the treatment list in front of the participant and ask whether the participant can name it. If the participant says no, the clinician will ask them what they should do next (circumlocute) and encourage them to do so. If the participant says yes, they will name the object and the clinician will ask the participant what they would have done *had they been unable* to name it (circumlocute) and encourage them to do so.
- (f) The clinician will encourage the participant to provide as many features as they can during circumlocution. This step engages the participant in *independent feature generation*, identified as the "active ingredient," of SFA³⁷.
- (g) The clinician will ask the participant to identify which of the strategy's components their description included (e.g., If they described a **dog** as, "an **animal** that **barks**," they would identify their description as having included the **category** and **action** strategy components). This step reinforces their knowledge of the strategy's components.

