During treatment data: During treatment, we will collect treatment session data and weekly probe data. Weekly probe data will be the exact same as the pre- and post-treatment naming and spontaneous speech probe data (naming accuracy, circumlocution attempts, verbatim transcriptions), in addition to strategy knowledge data probes (i.e., asking participants to identify as many of the six strategy components as possible). These weekly probes will occur once per week for the eight weeks of treatment. During the Strategy Education section of treatment, data will include quantification of strategy component knowledge (out of a possible six). During the Naming Treatment Plus Strategy Application section of treatment, data will include: Percent of items participant correctly identified whether they would be able to name the object before attempting to name it, naming accuracy before feature generation, number of features generated by the participant per item, number of correctly matched features with feature types per item, number of additionally identified feature types per item, and naming accuracy after feature generation. During the Strategy Debrief section of treatment, data will include: transcription of participant's reaction and opinion of treatment session and number of home-based opportunities identified by the participant in which they could use the strategy.

VI. BIOSTATISTICAL ANALYSIS

a. Specific data variables being collected for the study.

Cognitive-linguistic assessments (pre-treatment and post-treatment): Language and cognitive assessments will be scored based on standardized norms and methods of administration and scoring provided in testing manuals. Cognitive-linguistic assessments and inperson treatment sessions will be videotaped to provide a measure of reliability of scoring and administration of assessments and treatment.

Naming, spontaneous speech, and strategy knowledge probes (pre-treatment, during treatment, and post-treatment): We will collect (1) naming accuracy, (2) verbatim pre-naming verbal naming attempts, (3) verbatim responses to spontaneous speech probes, and (4) number of identified strategy components.

Treatment data: We will collect data on: (1) number of identified strategy components and (2) number of feature words during moments of naming difficulty.

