Aim 1b. Determine whether PWA learn the strategy and consequently demonstrate a change in their language behavior in moments of naming difficulty. Analyses: We will use visual inspection to examine participants' identification of the strategy components from Treatment Week 2, to Week 8, to post-treatment sessions. We will calculate effect sizes to measure the effect of treatment on the total number of feature words produced during naming assessments and on the average number of feature words produced per naming attempt during assessments, from pre- to post-treatment. Hypotheses: We expect that strategy training will result in participants' ability to identify all six strategy components by Week 8 and at least four of the strategy components during maintenance/retention sessions. We also hypothesize that strategy training will lead PWA to produce more feature words (i.e., engage in circumlocution) during moments of naming difficulty. Specifically, we expect to find medium to large effects on the number of feature words PWA produce during naming attempts.

Aim 2. Evaluate the effect of strategy training on patients' language production during connected speech. Statistical Analyses: We will calculate effect sizes to measure the effect of treatment on number of object words, feature words, CIUs, and CIUs/minute participants produce during connected speech tasks. Hypotheses: We hypothesize that strategy training will lead PWA to produce more object and feature words during connected speech. We expect medium to large effects on object words, feature words, CIUs, and CIUs/minute during connected speech from pre- to post-treatment.

Additional analyses: We will create mixed-effects models using treatment-phase data (e.g., strategy component identification) as fixed effects, and pre-treatment cognitive-linguistic measures (e.g., CLQT+ results) and participant characteristics (e.g., aphasia severity) as random effects to further understand post-treatment outcomes. We will calculate normalized change scores to measure participants' overall improvement relative to their baseline performance and maximum possible change⁵⁶. We will report changes between participants' pre- and post-treatment WAB-R Aphasia Quotient⁴⁶ scores using the benchmarks proposed by Gilmore and colleagues³³.

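### The strategy knowledge probe asks people with impaired naming to produce six components, with no recognition check, so a low score cannot separate not knowing the strategy from not retrieving the words

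*Combined protocol and SAP*

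**What the plan says.** Section V.a, item 2, describes a strategy knowledge probe in the weekly assessment, starting in Week 2, in which "the participant will be asked to provide the six strategy components". Item 4 repeats the probe at the one-month and two-month retention visits. Under Strategy Education, once a participant meets the progress rule, the clinician is to "ask the participant to list the components". Section V.e describes the weekly probe as "asking participants to identify as many of the six strategy components as possible". None of these places gives a response mode, a scoring rule or a recognition version.

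On the population, section I.a states that "all PWA experience one common impairment: naming", and III.a requires that eligible people "must also name 1-146 of the 176 items correctly on the initial administration".

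The score has two uses in VI.c. Under Aim 1b it is inspected visually, and the expectation is "ability to identify all six strategy components by Week 8", with four or more at retention. Under Additional analyses, mixed-effects models are built "using treatment-phase data (e.g., strategy component identification) as fixed effects". The opening of VI.c names the outcomes to be explained as post-treatment naming and connected speech. Aphasia severity and the pre-treatment cognitive-linguistic measures are listed as random effects. Baseline naming is not named as a fixed covariate.

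**The concern.** Providing or listing six components from memory is a word-production task, given to people selected for difficulty in producing words. If the score partly reflects retrieval, two readings become unsafe.

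- **Aim 1b.** A participant who understands all six components but cannot bring out the words is counted with one who never learned them. The thresholds of six and four then judge a mixture of knowledge and anomia. All participants get the same treatment, so no comparison group separates the two.
- **Exploratory models.** The score helps explain post-treatment naming. If both depend on naming ability, they can be associated even when strategy knowledge contributes nothing, and that association could be taken as support for the proposed mechanism.

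**Working it through.** The plan gives no figure to reproduce, and its sample size (20 recruited, 10 with complete data) does not bear on the point. The sums below show only how much retrieval could matter. The retrieval probabilities, variance shares and correlations are assumptions. From the plan come the six components, the thresholds of six and four, the sample sizes, and the eligible naming range of 1/176 = 0.6% to 146/176 = 83%.

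**1. Full knowledge, imperfect retrieval.** Suppose a participant knows all six and retrieves each independently with probability r. The score is Binomial(6, r), with mean 6r and P(all six) = r^6.

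| r | mean score | P(6 of 6) | P(at least 4) |
|---|---|---|---|
| 0.50 | 3.0 | 1.6% | 34% |
| 0.70 | 4.2 | 12% | 74% |
| 0.83 (146/176) | 5.0 | 33% | 93% |
| 0.95 | 5.7 | 74% | 99.8% |

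The link between r and object naming is unknown. If component words are 2 logits easier than objects (odds multiplied by e^2 = 7.4), object naming of 20%, 50% and 83% gives r = 0.65, 0.88 and 0.97. Mean scores are then 3.9, 5.3 and 5.8, and P(6 of 6) is 7.5%, 47% and 85%. At 20% object naming, P(at least 4) is 64%.

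**2. Shared naming ability.** In a simulation, naming ability was normal on the logit scale (mean 0, so 50% naming; SD 1). Knowledge was Binomial(6, 0.8) and independent of naming. Recall was Binomial(knowledge, retrieval probability), and the same ability drove naming. The correlation between recall score and naming was:

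| Component words easier than objects by | correlation |
|---|---|
| 0 logits | 0.66 |
| 2 logits | 0.43 |
| 3 logits | 0.25 |
| 4 logits | 0.12 |

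The knowledge score itself correlated 0.00.

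**3. What this could do at the planned size.** Let the score share a fraction w of its variance with retrieval, let the outcome correlate b with retrieval, and let knowledge have no effect. The spurious correlation is √w × b; for example, √0.5 × 0.8 = 0.57. I used a simple two-sided 5% test of association as a stand-in for the mixed model, with 20,000 runs per setting:

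| w, b | √w × b | false positives, n = 10 | false positives, n = 20 |
|---|---|---|---|
| 0, either b | 0 | 5% | 5% |
| 0.25, 0.5 | 0.25 | 10% | 19% |
| 0.25, 0.8 | 0.40 | 21% | 43% |
| 0.5, 0.5 | 0.35 | 16% | 34% |
| 0.5, 0.8 | 0.57 | 42% | 77% |

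Adjusting for baseline naming, assumed to correlate 0.9 with true retrieval, brings the four non-zero settings down to 5% to 8% at n = 10 and 6% to 13% at n = 20.

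**The case against.** The strongest reply is that the retrieval load is inferred. The plan does not say the answer must be spoken or match a set label, and it uses the looser verb *identify* as well as *provide* and *list*. The components are a closed set of six, taught for about 15 minutes each session and then applied to about eight objects, so they may be far easier to retrieve than pictured objects. This stands, and it is why the size is left open. It does not remove the point, because an unstated response mode and scoring rule leave the ambiguity in place.

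The plan also collects other evidence: feature-to-type matching in treatment sessions (V.e) and feature-word counts under Aim 1b. Component identification is only an example of a model predictor. This stands too. However, the matching score is not named in the Aim 1b analysis, and feature-word counts measure behaviour, not knowledge.

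Finally, recall may be the intended construct, since participants must start the strategy unaided at home. That is a good reason to keep recall and not to replace it with recognition, which may reach ceiling early.

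A reader might draw three stronger conclusions that the documents do not support:

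- **That a rising score merely shows a naming gain** (3.0 to 4.2 as retrieval goes from 0.50 to 0.70). This assumes object gains carry over to component words, which are not treatment objects. Section I.b says most restorative treatments do not help with unrelated items.
- **That a spurious association is bound to appear.** At n = 10 it reached significance in 10% to 42% of runs, a minority even in the worst setting tried.
- **That the naming results are compromised.** The models are additional analyses, and Aim 1a does not use the score.

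**Conclusion.** The point holds in a limited form. As described, the probe probably measures strategy knowledge together with some word retrieval, and nothing in the Aim 1b analysis pulls them apart. A score below six, or below four at retention, is therefore not evidence by itself that the strategy was not learned. In the exploratory models, part of any link between the score and post-treatment naming may be shared naming ability.

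The effect could be large if the component words are as hard to retrieve as object names (correlation 0.66 with no true link) and small if they are much easier (0.12 at 4 logits). The documents do not say where in that range the truth lies. These figures also rest on independent retrieval of the six words and on the assumed spread of naming ability. The Aim 1a effect sizes are untouched. The change is worth making because it is cheap and because the Aim 1b knowledge conclusion depends on it.

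**What to change.** 1. Keep the recall question as planned. State that written, gestured or paraphrased answers earn credit, and record the mode of each answer.
2. After recall, add a short recognition step in the same probe: the participant picks the six components from a set with foils (for instance 12 cards, six of them foils), read aloud or shown by screen share for remote participants. Score it separately, and record foils chosen as well as components: picking six of 12 at random gives 6 × 6/12 = 3 correct on average.
3. Report Aim 1b on both scores. Read low recall with high recognition as a retrieval failure, not a failure to learn.
4. In the exploratory models, enter baseline naming accuracy, which is already collected, as a fixed covariate. Show the results with the recognition score and with the session feature-to-type matching score as alternative predictors.

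The cost is one set of cards, some SAP wording and about two minutes per probe. On the V.a schedule (seven weekly probes from Week 2 to Week 8 and two retention visits), that is 9 × 2 = 18 minutes per participant. Recognition may reach ceiling, which would limit its value as a predictor. The cards also add slight exposure to the components; giving them after recall protects that day's recall score but not later ones.

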- General Health Questionnaire-12³⁵,
- Stroke and Aphasia Quality of Life Scale⁴¹,
- Subtests of the Cognitive Linguistic Quick Test-Plus (CLQT+)³⁹,
- The Metalanguage in Aphasia Assessment⁴⁰ (MetAphAs),
- The Communication Confidence Rating Scale for Aphasia (CCRSA),
- The Scenario Test⁸⁶

All assessments will be administered via paper and pencil, unless the participant is participating remotely. If they participate remotely, a fully encrypted device will be utilized but all responses will still be collected via paper and pencil.

b) Naming assessments and connected speech probes: Participants will complete three pretreatment naming assessments to establish a stable baseline⁸³ (*Figure 1*). During each baseline session, participants will complete a 176-item naming assessment and one connected speech probe. The 176-item naming assessment has objects from eight categories: animals, clothing, fruits and vegetables, occupations, household objects, other foods, tools. and transportation^{37,45,51}. Participants will be asked to name each object. To elicit connected speech, we will ask participants to verbally describe a picture, weekly activity, and/or personal memory (e.g., Tell me all about your weekend). Naming assessment and connected speech probe coding: We will calculate naming accuracy from the naming assessments and transcribe participants' prenaming verbalizations in order to later analyze and characterize their pre-treatment naming attempts. We will also transcribe and analyze participants' connected speech samples using Correct Information Unit (CIU) analysis⁶⁴, which provides measures of communicative efficiency and informativeness. Treatment and naming probe object selection: Participants' performance on the three pre-treatment naming assessments will determine which objects are either: trained during treatment, included in weekly naming probes, or untrained and used to test for deneralization post-treatment. Any objects a participant is unable to name on one, two, or three assessments will be included in the participant's object list. Of the included objects, we will create separate treatment and naming probe object lists taking into account the objects' semantic category and complexity.

Phase 2: Treatment

Each treatment session will have three sections:

- Strategy Education (~ 15 minutes),
- Naming Treatment Plus Strategy Application (~40 minutes),
- Strategy Debrief (~15 minutes).

Strategy Education. The clinician will:

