- (h) The clinician will ask the participant to identify which of the strategy's components were **not** included in their description (in this example, *description, location, association,* and *function*), and to generate one additional descriptive feature using the remaining strategy components. This step reinforces the strategy's components and gives the participant

additional opportunities for independent feature generation. The clinician will give the participant another opportunity to name the object if they had been unable to name it during **(e)** above.

This process (e - h) will be repeated for approximately eight treatment objects (~5 minutes per object). Alternate methods. If/when a participant is unable to independently produce any feature words about an object, the clinician will provide cues to guide them. Cues will be given from least to most facilitative, starting with general questions (e.g., *What does it do?*), to a binary choice (e.g., *Does it bark or meow?*), and eventually providing the correct feature response (e.g., *It barks.*)³⁷.

Strategy Debrief. The final portion of the session will include a debrief, which is regarded as a critical step in the learning process and enables learners to gain insight from direct experience and apply it to future situations^{52,77}.

- (j) The clinician will ask the participant for their reaction and opinion about the treatment session.
- (k) The clinician will provide positive reinforcement²⁶ by describing at least two instances during *Naming Treatment Plus Strategy Application* in which the participant effectively applied the strategy.
- (I) Finally, the clinician and participant will identify opportunities at home in which the participant could envision employing the strategy. The purpose of the debrief is to reinforce the strategy's applicability in all environments.

Phase 3 Post-treatment re-administration of assessments: Participants will complete the same cognitive-linguistic assessments, naming probes and spontaneous speech probes as they did pre-treatment within 20-30 days following the last treatment session.

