Phase 4 post-treatment tests of retention: Participants will attend two additional post-treatment sessions one month and two months after treatment completion to evaluate retention. During these study visits, participants will complete naming assessment and a connected speech connected speech task in which we will ask participants to verbally describe a picture, weekly activity, or personal memory description (e.g., *Tell me all about your weekend*).

- b. Drugs to be used: N/A
- c. Devices to be used: N/A
- d. Procedures/surgical interventions: N/A

e. Data to be collected and when data is to be collected

Pre- and post-treatment data: All pre-treatment and post-treatment cognitive-linguistic assessment data will be collected during pre- and post-treatment assessment sessions. This data will be collected on each respective assessment material's proper test booklet. Data from pre- and post-treatment naming probes will include naming accuracy and circumlocution attempts (i.e., naming attempts). Data from pre- and post-treatment spontaneous speech probes will include verbatim transcriptions of each participant's responses to the spontaneous speech probes (e.g., *Tell me all about your weekend*). Naming and spontaneous speech probe data will be collected

during the three pre-treatment and six post-treatment sessions. Audio recordings of naming probes will be randomized and coded for accuracy.

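### Re-assessment at 20-30 days can fall on or beside the one-month retention visit, which may then add little about naming retention

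*Combined protocol and SAP*

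**What the plan says.** **Re-administration.** The study sequence in Section V.a has the full assessment set repeated "as they did pre-treatment within 20-30 days following the last treatment session", in sessions spread over an average of 3-5 days. Phase 3 of the same section repeats the timing: "pre-treatment within 20-30 days following the last treatment session".

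**Retention.** The next step in the sequence reads: "Participants will attend two additional post-treatment sessions one month and two months after the final treatment session". Each of these visits includes the 176-item naming assessment. The detailed description, headed "Phase 4 post-treatment tests of retention", again places the visits "one month and two months after treatment completion to evaluate retention". Neither place gives a window in days.

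**Measurements during treatment.** From Week 2, the first session of each week opens with an assessment "consisting of a naming probe, a connected speech probe, and a strategy knowledge probe".

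**Object lists.** Phase 1 b) sorts objects by whether they are "trained during treatment, included in weekly naming probes, or untrained and used to test for" generalization after treatment, and adds that "we will create separate treatment and naming probe object lists".

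**Analysis.** Section VI.c builds each effect size from a participant's average scores before and after treatment, but does not list the sessions that enter the post-treatment average. The only retention hypothesis there with a numerical target concerns strategy components: at least four at the retention sessions.

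**The concern.** The plan treats re-administration and retention testing as two steps with different purposes: the first gives the post-treatment score, the second shows whether gains last. Both are timed from the last treatment session. The upper end of the re-administration window is about where the first retention visit falls. A retention visit has to be some distance in time from the score it is compared with. If the two are days apart, stability between them is close to a test-retest result and says little about whether a gain is kept.

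Naming of generalization objects is the outcome most exposed, because for some of those objects the text shows no earlier score after baseline that could serve as the reference. Generalization is the stated purpose of the trial, so a reader will look for evidence that gains on these objects persist. The label on the score also matters: one taken 20-30 days after treatment is not an immediate gain.

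**Working it through.** The plan states no interval between the two visits, so there is no figure of its own to reproduce. The interval follows from the stated timings.

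**Inputs**
- Re-administration day R: 20 to 30 days after the last session (V.a, study sequence and Phase 3).
- One-month visit M1: no days given. Assumed 28 to 31.
- Two-month visit M2: no days given. Assumed 56 to 62.
- Spread of re-administration: an average of 3-5 days (V.a).

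**Gap to the one-month visit, M1 − R**
- Month of 28 days: 28 − 30 = −2 to 28 − 20 = 8.
- Month of 30 days: 30 − 30 = 0 to 30 − 20 = 10.
- Month of 31 days: 31 − 30 = 1 to 31 − 20 = 11.

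A negative gap would put the retention visit before re-administration, against the numbered order in V.a. Keeping that order, the gap is 0 to 11 days. Even at its earliest, re-administration comes 20/31 = 65% of the way to the one-month visit.

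**Effect of the 3-5 day spread** (taking consecutive days)
- Starting on day 30: ends on day 30 + 3 − 1 = 32 to 30 + 5 − 1 = 34, after a visit at day 28-31.
- Finishing by day 30: starts on day 30 − 3 + 1 = 28 or 30 − 5 + 1 = 26, which is on or next to the one-month visit.

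**Gap to the two-month visit, M2 − R**
- Smallest: 56 − 30 = 26 days. Largest: 62 − 20 = 42 days. This visit stays distinct.

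**Which outcomes have a late-treatment reference**
- Strategy knowledge and connected speech: weekly probes to Week 8, so retention can be set against Week 8.
- Trained objects: V.e records naming accuracy in treatment sessions before features are generated.
- Weekly-probe objects: named weekly from Week 2.
- Objects on neither list, kept to test generalization: nothing in the visible text specifies a measurement between baseline and re-administration. V.e describes the weekly probe data as matching the pre- and post-treatment data, but what it lists there are types of data, not items.

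For the last group, the score at day 20-30 is both the first result after baseline and the only reference for the one-month visit.

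**The case against.** The best reply is that no stated naming hypothesis depends on the one-month visit. Aim 1a compares pre- with post-treatment. The one numerical retention target concerns strategy components and can be read against Week 8. A gain still present at 20-30 days is, if anything, firmer evidence of lasting generalization than one measured the day after treatment. All of this stands, and it keeps the point minor. What remains is that a visit scheduled to evaluate retention may nearly repeat the score before it.

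Four stronger readings are tempting, and the documents do not support them:

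- **All untrained objects lack a late-treatment measurement.** A reader might infer this from the three-way split of objects. But the treatment and weekly-probe lists are described as separate, so objects on the probe list appear to be untreated and are named weekly. The gap applies only to objects on neither list.
- **The 20-30 days is an upper limit**, so that one participant's score is immediate and another's is a month old. An upper limit needs one number and the text gives two. A range is the natural reading.
- **The retention visits are averaged into the post-treatment score.** V.a does call them post-treatment sessions, and VI.c does not list the averaged sessions. However, the phase headings and the separate mention of maintenance/retention sessions under Aim 1b favour re-administration only. This is missing detail, not evidence that effect sizes will be diluted.
- **The six post-treatment sessions in V.e conflict with the schedule.** Three repeated naming sessions plus two retention visits make five, but Figure 1 is not shown and may itemise six. No contradiction can be claimed.

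Figure 1 may also show visit timing. That limits confidence, but the written timings, which appear twice each, would still need to agree with it.

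**Conclusion.** The point holds in a limited form and is minor. Followed as written, the plan allows 0 to 11 days between re-administration and the one-month retention visit, and the two can coincide or overlap once the 3-5 day spread is counted. The one-month visit may then add little about naming retention, above all for generalization objects on neither the treatment list nor the weekly-probe list.

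This rests on reading 20-30 days as a range, taking a month as 28 to 31 days, and keeping the numbered order of visits. The Aim 1a contrast, the strategy-knowledge retention hypothesis and the two-month visit, 26 to 42 days after re-administration, are unaffected. Retention evidence for naming is weakened at one time point, not removed. The unnamed sessions in the post-treatment average are a separate, small clarification.

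**What to change.** Reconcile the study sequence, Phase 3 and Phase 4 in Section V.a, and bring Figure 1 into line. There are two ways to do it:

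1. Give re-administration and each retention visit its own window, in days since the last treatment session, with no overlap. State that the re-administration window covers the whole 3-5 day spread.
2. Keep the 20-30 day window. Report that score as about one-month maintenance, not immediate gain, and base naming-retention claims on the two-month visit. The one-month visit is then read as a near repeat.

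As a minor clarification, state in Section VI.c that the average post-treatment score is the mean over the re-administration sessions, and that the one- and two-month visits are reported separately. Use the same two labels in the Aim 1b text.

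The cost is small: existing assessment visits may move under the first option, or a claim is relabelled under the second. Neither adds a visit.
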